11.1.4.4 Duration of Response

Duration of overall response: The duration of overall response is measured from the time measurement criteria are met for CR or PR (whichever is first recorded) until the first date that recurrent or progressive disease is objectively documented (taking as reference for progressive disease the smallest measurements recorded since the treatment started). The duration of overall CR is measured from the time measurement criteria are first met for CR until the first date that recurrent disease is objectively documented.

Duration of stable disease: Stable disease is measured from the start of the treatment until the criteria for progression are met, taking as reference the smallest measurements recorded since the treatment started.

12 Data Reporting / Regulatory Requirements

Adverse event lists, guidelines, and instructions for AE reporting can be found in [Section 7](#).

12.1 Data Reporting

12.1.1 Method

This study will be monitored by the Clinical Data Update System (CDUS) version 3.0. Cumulative CDUS data will be submitted quarterly to CTEP by electronic means. Reports are due January 31, April 30, July 31, and October 31. Instructions for submitting data using the CDUS can be found on the CTEP Web site (<http://ctep.cancer.gov>).

Note: All adverse events that have occurred on the study, including those reported through CTEP-AERS, must be reported via the monitoring method identified above.

12.1.2 Responsibility for Submission

Study participants are responsible for submitting CDUS data and/or data forms to the Coordinating Center quarterly to allow time for Coordinating Center compilation, Principal Investigator review, and timely submission to CTEP (see [Section 12.1.1](#)). The Coordinating Center is responsible for compiling and submitting CDUS data to CTEP for all participants and for providing the data to the Principal Investigator for review.

12.2 Data Safety and Monitoring Plan

The investigators at each participating center will be responsible for the collection, maintenance, and quality control of the study data. Adverse events observed in patients enrolled on the trial will be monitored in real time by the Principal and Associate Investigators, and attribution of these events to the research will be determined at the end of each treatment cycle in each subject. The clinical research team (PI, adjunct PI, research nurses, data managers) will meet weekly when patients are being actively treated on the trial to discuss each patient in detail and ensure that all events are graded appropriately, and that the attribution to study drug is correct. The Coordinating Center is responsible for establishing conference calls between participating sites at least on a monthly basis to discuss the observed toxicities and protocol issues.

All SAEs will be reported through CTEP-AERS to CTEP, to the Coordinating Center PI at NCI, and forwarded to the IRB per [Section 7](#). In all cases where the dose of the study treatment has been reduced/modified or the patient withdrawn due to unusual or unusually severe toxicity considered related to the study treatment, the investigator must contact and inform the Coordinating Center PI. All sites will be monitored by the CTEP drug monitor who will receive data from all participating sites.

Data will be monitored regularly by the principal investigator in order to identify significant toxicity trends. Any new significant finding that may affect the patient's willingness to continue in the study will be shared with patients.

Confidentiality will be maintained as much as possible, consistent with applicable regulations. Names of participants or identifying material will not be released without patient permission, except when such release is required by law. No patient's name or identifying information will be released in any publication or presentation. Records are maintained according to current legal requirements, and are made available for review according to the requirements of the FDA or other authorized user, only under guidelines established by the Federal Privacy Act.

Safety Monitoring Committee:

Because this is a multi-institutional Phase II protocol for which the Developmental Therapeutics Clinic (DTC), NCI is the Coordinating Center, it will be monitored by the DTC Safety Monitoring Committee, NCI. Reviews will occur annually concurrent with NCI IRB continuing reviews.

12.3 Multicenter Guidelines

This protocol will open initially at the NCI. The NCI IRB will be notified once the participating centers' IRBs have approved the studies to open. This protocol will follow the CCR's Clinical Research Operations' SOPs for multicenter trials.

12.3.1 IRB Approvals

As the Coordinating Center for a trial, it is the PI's responsibility to ascertain that no patients are entered on the trial at a participating institution without full IRB approval. Thus, the NCI IRB must approve the addition of each participating institution to the protocol and will require a copy of the local IRB approval from each participating institution before NCI IRB approval will be granted.

The PI will provide the NCI IRB with a copy of the participating institution's approved yearly continuing review. Registration will be halted at any participating institution in which a current continuing approval is not on file at the NCI IRB.

12.3.2 Amendments and Consents

The NCI PI will provide the NCI IRB with copies of all amendments, consents and approvals from each participating institution.

12.3.3 Data Collection

The investigators will be responsible for the collection, maintenance, and quality control of the study data. All data collected for each study subject will be entered into the Cancer Central Clinical Database (C3D), an NCI electronic case report form/database, every 2 weeks. The participating sites will be able to enter the data remotely into the web-based C3D system. Each site investigator is also responsible for maintaining all source documentation related to the study, including any films, tracings, computer discs or tapes. NCI will be responsible for data management, data analysis, and reporting. Data collection forms will be provided to the participating institutions. Required data

include, not exclusively: prior disease-related therapies with dates, disease type, stage, disease sites, with measurements, and concurrent medications.

12.3.4 Data and Center Audits

Audits will be conducted yearly to ensure data integrity and provide quality control. These audits will be conducted by the NCI research team. Selected patient charts should be audited as well as the participating institution's Standard Operating Procedures (SOP) at the time of the visit. Data from participating institutions should be available when the protocol is audited at the NCI.

12.3.5 CTEP Multicenter Guidelines

This protocol will adhere to the policies and requirements of the CTEP Multicenter Guidelines. The specific responsibilities of the Principal Investigator and the Coordinating Center (Study Coordinator) and the procedures for auditing are presented in [Appendix C](#).

- The Principal Investigator/Coordinating Center is responsible for distributing all IND Action Letters or Safety Reports received from CTEP to all participating institutions for submission to their individual IRBs for action as required.
- Except in very unusual circumstances, each participating institution will order DCTD-supplied agents directly from CTEP. Agents may be ordered by a participating site only after the initial IRB approval for the site has been forwarded by the Coordinating Center to the CTEP PIO ([contact]) (except for Group studies).

12.4 Cooperative Research and Development Agreement (CRADA) / Clinical Trials Agreement (CTA)

N/A

13 Statistical Considerations

The primary objective of this protocol is to determine if FdCyd/THU is associated with adequate response rates (RR) or progression-free survival (PFS) in patients with any of a variety of malignancies as defined below. PFS will be estimated using a Kaplan-Meier curve. The results obtained will be informally compared to those from other studies in similar patients to help determine the potential benefit of exploring use of these agents in a subsequent, more definitive study, if warranted. These patients will have been previously treated with multiple prior chemotherapeutic regimens, so that any reasonable evidence of benefit will be interpreted as being a positive indicator.

Exploratory study objectives relate to the safety of the agents in patients with various solid tumors, and an evaluation of the impact of FdCyd/THU on extent of LINE-1 methylation in tumor biopsies. Blood samples will also be collected to evaluate the number of circulating tumor cells before and during treatment. Changes from baseline will be determined in either

absolute or relative terms as appropriate, and evaluated for statistical significance, as well as to determine if the changes or the actual values at a time point are associated with clinical response. Paired comparisons with baseline will be done using a paired t-test or Wilcoxon signed rank test as appropriate, and the changes will be compared between responders and non-responders (PD) using a two-sample t-test (adequate numbers of subjects with normally distributed data in both groups) or a Wilcoxon rank sum test, if enough patients respond for this to be appropriate. In all such cases, these analyses will be considered exploratory and not formally adjusted for multiple comparisons. However, to ensure proper interpretation in the context of a potentially large number of explorations being performed, only p values <0.01 will be interpretable as being associated with statistical significance.

Patients will be enrolled into one of 4 strata as follows:

- A Non-Small Cell Lung Cancer
- B Breast Cancer
- C Urothelial Transitional Cell Carcinoma
- D Head and Neck Cancer

In each stratum, the study will be conducted with a dual-endpoint design, based on RR and 4-month (6-month for the breast cancer stratum) PFS as co-primary endpoints. In strata A, C, and D, evidence of positive results is sought in the first stage to determine if the particular stratum should be expanded into the second stage. In stratum B, a one-stage design is utilized. Also, throughout the sections below, 'response' will refer to the appearance of a positive outcome as defined for each disease.

Stratum A: Non-Small Cell Lung Cancer

Stratum A will use a trial design for patients with NSCLC that judges the agents as promising if we achieve either tumor response rates of 20% vs. 5% or 4-month PFS rates of 50% vs. 25% (corresponding to median PFS of 4 vs. 2 months). The design requires a maximum of 45 evaluable patients. For each stratum, if at least 6 objective responses (at least 13%), or at least 18 instances of 4-month PFS (at least 40%), are observed among the 45 evaluable patients, this regimen will be considered worthy of further testing in this disease. If no more than one objective response (no more than 5%), and no more than 6 instances of 4-month PFS (no more than 30%), are observed among the initial 20 patients, the stratum will be terminated early and declared negative.

This design yields at least 87% power to detect a true objective response rate of at least 20%. It yields at least 90% power to detect a true 4-month PFS rate of at least 50% (median PFS of 4 months). It yields at least .96 probability of a negative result if the true objective response rate is no more than 5% and the true 4-month PFS rate is no more than 25% (median PFS of 2 months), with approximately .58 probability, at least, of early negative stopping in this case. In addition, the over-all probability of negative results across all 4 strata, under the over-all null hypothesis, is .85. These last three probabilities are calculated assuming that tumor response rate and PFS rate are uncorrelated. If they are positively correlated, as is likely, the probabilities will be a bit higher.

Stratum B: Breast Cancer

Stratum B will use a trial design for patients with breast cancer that judges the agents as promising if we achieve either tumor response rates of 20% vs. 5% or 6-month PFS rates of 50% vs. 25% (corresponding to median PFS of 6 vs. 3 months). The design requires a maximum of 35 evaluable patients. If at least 5 objective responses (at least 14%), or at least 15 instances of 6-month PFS (at least 43%), are observed among the 35 evaluable patients, this regimen will be considered worthy of further testing in this disease. This design yields at least 85% power to detect a true objective response rate of at least 20%. It yields at least 84% power to detect a true 6-month PFS rate of at least 50% (median PFS of 6 months). It yields at least .95 probability of a negative result if the true objective response rate is no more than 5% and the true 6-month PFS rate is no more than 25% (median PFS of 3 months). In addition, the over-all probability of negative results across all 4 strata, under the over-all null hypothesis, is .85. These last three probabilities are calculated assuming that tumor response rate and PFS rate are uncorrelated. If they are positively correlated, as is likely, the probabilities will be a bit higher.

If accrual onto this stratum is slow, and the target to demonstrate promising response rate (5 responders) or PFS rate (15 patients with 6-month PFS) has already been met among the initial 30 patients, consideration will be given to stopping the trial and declaring the regimen promising. The likelihood of demonstrating such promise under the alternative hypothesis is at least .57.

Stratum C: Urothelial Transitional Cell Carcinoma

Stratum C will use a trial design for patients with urothelial transitional cell carcinoma that judges the agents as promising if we achieve either tumor response rates of 20% vs. 5% or 4-month PFS rates of 50% vs. 25% (corresponding to median PFS of 4 vs. 2 months). The design requires a maximum of 45 evaluable patients. If at least 6 objective responses (at least 13%), or at least 18 instances of 4-month PFS (at least 40%) are observed among the 45 evaluable patients, this regimen will be considered worthy of further testing in this disease. If no more than one objective response (no more than 5%), and no more than 6 instances of 4-month PFS (no more than 30%), are observed among the initial 20 patients, the stratum will be terminated early and declared negative.

This design yields at least 87% power to detect a true objective response rate of at least 20%. It yields at least 90% power to detect a true 4-month PFS rate of at least 50% (median PFS of 4 months). It yields at least .96 probability of a negative result if the true objective response rate is no more than 5% and the true 4-month PFS rate is no more than 25% (median PFS of 2 months), with approximately .58 probability, at least, of early negative stopping in this case. In addition, the over-all probability of negative results across all 4 strata, under the over-all null hypothesis, is .85. These last three probabilities are calculated assuming that tumor response rate and PFS rate are uncorrelated. If they are positively correlated, as is likely, the probabilities will be a bit higher.

Stratum D: Head and Neck Cancer

Stratum D will use a trial design for patients with head and neck cancer that judges the agents as promising if we achieve either tumor response rates of 20% vs. 5% or 4-month PFS rates of 50% vs. 25% (corresponding to median PFS of 4 vs. 2 months). The design requires a maximum of 45 evaluable patients. If at least 6 objective responses (at least 13%), or at least 18 instances of 4-month PFS (at least 40%), are observed among the 45 evaluable patients, this regimen will be considered worthy of further testing in this disease. If no more than one objective response (no more than 5%), and no more than 6 instances of 4-month PFS (no more than 30%) are observed among the initial 20 patients, the stratum will be terminated early and declared negative.

This design yields at least 87% power to detect a true objective response rate of at least 20%. It yields at least 90% power to detect a true 4-month PFS rate of at least 50% (median PFS of 4 months). It yields at least .96 probability of a negative result if the true objective response rate is no more than 5% and the true 4-month PFS rate is no more than 25% (median PFS of 2 months), with approximately .58 probability, at least, of early negative stopping in this case. In addition, the over-all probability of negative results across all 4 strata, under the over-all null hypothesis, is .85. These last three probabilities are calculated assuming that tumor response rate and PFS rate are uncorrelated. If they are positively correlated, as is likely, the probabilities will be a bit higher.

For all strata, toxicity data will be obtained, and if there are 5 or more patients in a given stratum who experience Grade 3 or greater toxicity attributable to the agent, then comparisons between cohorts across grades of toxicity may be done using a Kruskal-Wallis test for ordered columns. Otherwise, toxicities will be tabulated and described.

Comparisons between extent of LINE-1 methylation and γ - to β -globin ratio will be made by subtracting pre-treatment from post-treatment levels and determining the statistical significance of the difference using a Wilcoxon signed rank test. These measures will all be evaluated with exploratory intent, and findings will be reported without formal adjustment for multiple comparisons, but in the context of a study with multiple exploratory analyses performed.

A total of 160 evaluable patients may be required if the study enrolls patients onto the second stage of cohorts A and D. The diseases studied are quite different from one another; thus, imposing an overall rule about responses in the full spectrum of patients, prior to enrolling to the first stage is not practical.

To allow for inevaluable patients, a total of 165 patients will be set as the accrual ceiling. It is anticipated that approximately 8-9 patients per month will be accrued such that approximately 21 months will be required to accrue up to 165 patients.

14 References

1. Lapeyre, J.N. and F.F. Becker, *5-Methylcytosine content of nuclear DNA during chemical hepatocarcinogenesis and in carcinomas which result*. Biochem Biophys Res Commun, 1979. **87**(3): p. 698-705.
2. Herman, J.G. and S.B. Baylin, *Gene Silencing in Cancer in Association with Promoter Hypermethylation*. N Engl J Med, 2003. **349**(21): p. 2042-2054.
3. Jemal, A., et al., *Cancer statistics, 2008*. CA Cancer J Clin, 2008. **58**(2): p. 71-96.
4. Greenberg, P.A., et al., *Long-term follow-up of patients with complete remission following combination chemotherapy for metastatic breast cancer*. J Clin Oncol, 1996. **14**(8): p. 2197-205.
5. Wilcken, N. and R. Dear, *Chemotherapy in metastatic breast cancer: A summary of all randomised trials reported 2000-2007*. European Journal of Cancer, 2008. **44**(15): p. 2218-2225.
6. Chew, H.K., et al., *Phase II Studies of Gemcitabine and Cisplatin in Heavily and Minimally Pretreated Metastatic Breast Cancer*. J Clin Oncol, 2009: p. JCO.2008.17.4839.

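### The stratum maxima add to 170 evaluable patients: the stated total of 160 fits no outcome of the design, and the ceiling of 165 is 5 short if strata A, C and D all expand

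*Combined protocol and SAP*

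**What the plan says.** All of this is in Section 13, Statistical Considerations.

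- The design paragraph makes three strata two-stage: "In strata A, C, and D, evidence of positive results is sought in the first stage". Stratum B (breast) has one stage.
- For each of A (lung), C (urothelial) and D (head and neck): "The design requires a maximum of 45 evaluable patients". Each closes as negative after its first 20 patients if there is at most one response and at most six 4-month PFS successes. The stated chance of this under the null is given as "with approximately .58 probability, at least, of early negative stopping in this case".
- For B: "The design requires a maximum of 35 evaluable patients". If accrual is slow and a target has already been met, stopping at 30 may be considered.
- Near the end of the section: "A total of 160 evaluable patients may be required if the study enrolls patients onto the second stage of cohorts A and D".
- Then: "To allow for inevaluable patients, a total of 165 patients will be set as the accrual ceiling", with "approximately 21 months will be required to accrue up to 165 patients" at 8 to 9 per month. The Design part of the Précis repeats 165 as the maximum across all centers.

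**The concern.** The total and the ceiling do not follow from the stratum sizes. The sentence giving 160 names A and D as the strata that may expand and omits C. The ceiling is presented as including room for inevaluable patients, yet it is smaller than the number of evaluable patients the four designs can call for.

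The ceiling is an enrolment limit. If it binds, at least one stratum ends below its planned size, and the plan does not say which one gives way or what cut-offs then apply. That choice would be made after stage 1 results are known. The outcome in which this happens, all three two-stage strata continuing, is the one to expect if the drug works broadly.

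**Working it through.** **1. Inputs (Section 13).** A, C, D: first stage 20, maximum 45; stop if ≤1 response and ≤6 PFS successes; positive if ≥6 responses or ≥18 PFS successes. B: 35, positive if ≥5 or ≥15. Null rates 5% (response) and 25% (PFS); alternatives 20% and 50%. Stated total 160, ceiling 165.

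**2. Are the stratum sizes the operative ones?** Exact binomial calculation, endpoints independent as the plan assumes.

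- Early stop under the null: P(X≤1 | 20, 0.05) × P(Y≤6 | 20, 0.25) = 0.7358 × 0.7858 = 0.578 (stated .58).
- Power on one endpoint, requiring that endpoint itself to pass stage 1: Σ over x from 2 to 20 of b(x; 20, 0.20) × P(Bin(25, 0.20) ≥ 6−x) = 0.872 (stated 87%). For PFS, with x from 7 and target 18 at rate 0.50: 0.899 (stated 90%).
- Negative result under the null, continuing on either endpoint: 0.962 (stated .96).
- B at n=35: 0.857 and 0.845 (stated 85% and 84%); negative under the null 0.956 (stated .95).
- All four strata negative under the null: 0.962³ × 0.956 = 0.851 (stated .85).

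The sizes 45, 35, 45, 45 reproduce the stated properties, so as written the total and the ceiling are the figures out of line.

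**3. Every total the nominal sizes allow.** A, C and D are each 20 or 45.

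| Strata expanding among A, C, D | B = 35 | B = 30 |
|---|---|---|
| none | 95 | 90 |
| one | 120 | 115 |
| two | 145 | 140 |
| three | 170 | 165 |

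None is 160. A and D expanding with C stopped gives 45 + 35 + 20 + 45 = 145. Section 4.1 letters the strata differently (D is breast there), but that does not help, because breast has no second stage.

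**4. The ceiling.** With all three expanded, 165 − 170 = −5 before any inevaluable patient. With B stopped at 30, 165 − 165 = 0. In every other outcome at most 145 are needed, so 165 suffices up to an inevaluable rate of 1 − 145/165 = 12%.

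**5. How often it binds.** Chance that one stratum passes stage 1: 1 − 0.578 = 0.422 under the null; 0.946 if active on response only; 0.958 on PFS only; 0.996 on both. Multiplying over A, C and D, taken as independent:

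| Active strata among A, C, D | P(all three expand) |
|---|---|
| none | 0.075 |
| one | 0.17–0.18 |
| two | 0.38–0.42 |
| three | 0.85–0.99 |

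Low ends: active on one endpoint. High ends: active on both.

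**6. Cost once it binds, cut-offs unchanged.** Single-endpoint power as in step 2; false-positive rate for either endpoint.

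| Stratum size | Response | PFS | False positive |
|---|---|---|---|
| A/C/D, n=45 (planned) | 0.872 | 0.899 | 3.8% |
| n=43–44 (5 lost, shared over the three) | 0.85–0.86 | 0.86–0.88 | |
| n=40 (5 lost, one stratum) | 0.815 | 0.774 | 1.7% |
| n=35 (10 lost, one stratum) | 0.718 | 0.499 | 0.8% |
| B, n=35 (planned) | 0.857 | 0.845 | 4.4% |
| B, n=30 (5 lost) | 0.745 | 0.572 | 1.8% |

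A loss of 10 corresponds to 5 inevaluable patients, the gap between the plan's own 160 and 165.

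**7. Inevaluable patients.** The plan gives no rate. At assumed rates of 3%, 5% and 10%, 165 enrolled yield 160.0, 156.8 and 148.5 evaluable, which is 10, 13 and 22 short of 170. Enrolment needed is 170/(1 − q): 176, 179 and 189.

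**The case against.** The sum of 170 is not in dispute; the objections concern how much it matters.

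- **Power with both endpoints active.** The 0.99 chance of full expansion assumes activity on both endpoints, while the losses in step 6 are for one endpoint. Under the plan's either/or rule with both active, power in A, C or D is 0.991 at n=45, 0.963 at n=40 and 0.863 at n=35. Losing 5 patients then costs about 3 points. This stands. The larger losses belong to activity on a single endpoint, where the chance of full expansion is 0.85 to 0.88 if all three strata are active.
- **The loss is conditional.** If only one stratum is active and it absorbs all 5, its power averaged over all outcomes moves only from 0.880 to 0.869 (response) or from 0.908 to 0.884 (PFS). This also stands. (These baselines let a stratum continue on either endpoint; the 0.872 and 0.899 in step 2 require the same endpoint to pass. The difference is about 0.01.)
- **Totals are nominal.** No pause in accrual is specified while 4-month PFS matures in the first 20, so a stopped stratum could exceed 20. That is fair, but it does not turn 160 into a planned total.
- **Evaluability.** Section 11.1.1 counts patients who progress before the end of cycle 1 as evaluable, which limits the inevaluable loss. The 5% and 10% rates are assumptions.
- **Late version.** The text refers to 2017 and 2018 and reports marker data on 52 patients from this trial. Accrual and stage 1 status are not given, so whether the ceiling can still be changed before it binds cannot be judged from the documents.

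None of these reconciles 160 or 165 with the stratum maxima.

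**Conclusion.** The concern holds. On the plan's own sizes the evaluable maximum is 170. The stated 160 is 10 too low as a maximum and 15 too high for the outcome it describes. The ceiling is 5 below the evaluable maximum with no allowance left; B's discretionary stop at 30 only brings the need to exactly 165.

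The total of 160 equals 45 + 35 + 35 + 45, which would fit a urothelial stratum of 35 with no interim stop. That is inference from arithmetic alone. No section states such a design, and the overall negative probability would hardly distinguish it: 0.962² × 0.956² = 0.845 against 0.851.

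The point should be fixed but is contained. The ceiling matters in one outcome only. Each stratum's design and decision rule is sound, and with fixed cut-offs a shorter stratum has a lower false-positive rate. What is lost is power, by an amount that depends on which stratum gives way. The probabilities assume independent strata and endpoints; the power losses at 40 and 35 assume one stratum takes the whole shortfall.

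**What to change.** Replace the sentence in Section 13 with wording to this effect: if strata A, C and D all enter the second stage, the study needs 170 evaluable patients. Confirm that C's maximum is 45. Then reconcile the ceiling in Section 13 and the Précis in one of two ways.

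**(a) Raise the ceiling** to 170 plus an allowance from a stated inevaluable rate. A ceiling of 175 merely keeps the implied 5; assumed rates of 3%, 5% or 10% give 176, 179 or 189. At 8 per month, accrual would take about 22, 22.4 or 23.6 months, against 165/8 = 20.6 now. This adds 10 to 24 places and roughly 1 to 3 months, used only if all three strata expand.

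**(b) Keep 165**, state that it cannot fill all four strata, and name in advance which one may close short, with cut-offs and properties at the evaluable size reached. Examples for A, C or D:

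| n | Cut-offs (response / PFS) | False positive | Response power | PFS power |
|---|---|---|---|---|
| 40 | ≥6 / ≥16 | 3.6% | 82% | 89% |
| 35 | ≥5 / ≥14 | 6.0% | 83% | 89% |
| 35 | ≥5 / ≥15 | 4.2% | 83% | 83% |

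This adds no patients. It accepts lower response power in the named stratum, and at n=35 a false-positive rate above the 4% implied by the stated .96.
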